### **9.5.2. Other Safety Evaluations**

Safety will be measured by adverse events, laboratory test results, ECGs, vital sign measurements, physical examination findings, and assessment of ECOG performance status score. All toxicities will be graded according to the NCI-CTCAE Version 4. Any clinically relevant changes occurring during the study must be recorded on— the Adverse Event section of the eCRF. Any clinically significant abnormalities persisting at the end of the study/early withdrawal will be followed by the investigator until resolution or until a clinically stable endpoint is reached. A QTc substudy will be conducted in a subpopulation of subjects at selected sites.

Based on the previous human experience with daratumumab, in vitro studies, and animal toxicological findings, IRRs/allergic reactions, infection, hemolysis, and thrombocytopenia will be closely monitored. As a biologic agent, immunogenicity also will be monitored. Any of the safety monitoring assessments may be performed more frequently, and AEs should be evaluated by the investigator according to the standard practice, if clinically indicated.

### **Adverse Events**

Adverse events (with the exception of progression of MM) will be reported by the subject (or, when appropriate, by a caregiver, surrogate, or the subject's legally acceptable representative) for the duration of the study. Adverse events will be followed by the investigator as specified in [Section 12](#), Adverse Event Reporting.

### **Clinical Laboratory Tests**

As of Amendment 5, refer to [Attachment 4](#) for a description of study procedures for subjects who continue in the Treatment Extension Phase or who have discontinued treatment but remain in Follow-up.

Blood samples for serum chemistry and hematology will be collected. The investigator must review the laboratory report, document this review, and record any clinically relevant changes occurring during the study in the AE section of the eCRF. The laboratory reports must be filed with the source documents.

The tests below will be performed by the local laboratory unless otherwise noted.

- Hematology Panel
  - hemoglobin
  - white blood cell (WBC) count with absolute neutrophils and lymphocytes
  - platelet count
- Serum Chemistry Panel
  - uric acid
  - total bilirubin a
  - creatinine b
  - blood urea nitrogen (BUN)
  - aspartate aminotransferase (AST)
  - alanine aminotransferase (ALT)
  - alkaline phosphatase
  - lactate dehydrogenase (LDH)

At Screening and during Cycle 1 only, before the second through eighth infusions of daratumumab

- potassium
- calcium
- sodium
- magnesium

- a. direct bilirubin if Gilbert's disease
- b. calculate creatinine clearance; please refer to Section 9.2.1.4.

### HBV serology

For subjects who enter extension treatment period, HBV serology (HBsAg, anti-HBs, and anti-HBc) testing is to be performed locally prior to re-initiation. HBV serology is not required at re-initiation if this was performed as part of standard of care within 3 months prior to the re-initiation or the start of extension treatment is within 3 months of last daratumumab dose. For subjects with evidence of positive HBV serology, monitor for clinical and laboratory signs of HBV reactivation during treatment (Q12W), and for at least 6 months (Q12W) following the end of study treatment.

### HBV DNA test

Subjects who are positive for Anti-HBc or Anti-HBs will undergo testing for hepatitis B DNA by PCR. Subjects with serologic findings suggestive of HBV vaccination (Anti-HBs positivity as the only serologic marker) and a known history of prior HBV vaccination do not need to be tested for HBV DNA by PCR. During and following study treatment, subjects who have history of HBV infection will be closely monitored for clinical and laboratory signs of reactivation of HBV as specified in the Time and Events Schedule (Table 1). Where required by local law, the results of HBV testing may be reported to the local health authorities.

**Serum or urine pregnancy testing**

For women of childbearing potential only, serum or urine pregnancy test at screening and as clinically indicated.

**Calcium and albumin adjusted calcium:**

These parameters will be part of the efficacy evaluations as specified in Section 9.2.1.4 and will be analyzed by the central laboratory. Measurement of calcium and albumin should follow the schedule for disease assessments.

**Hemoglobin and creatinine**

These parameters will be part of the efficacy evaluations as specified in Section 9.2.1.4 and will be analyzed by the local laboratory. At screening and during treatment, these parameters are part of the safety laboratory assessments. After end of treatment, subjects who stopped before PD will continue to have these parameters evaluated locally with each disease assessment.

**β-2 microglobulin**

β-2 microglobulin will be assessed at screening and upon disease progression, as part of efficacy evaluations. Sample will be analyzed by the central laboratory.

**Daratumumab Interference with Indirect Antiglobulin Test (IAT) results**

Daratumumab interferes with the Indirect Antiglobulin Test (IAT), which is a routine pre-transfusion test performed to identify a patient's antibodies to minor antigens so that suitable donor blood can be given for transfusion. Daratumumab does not interfere with ABO/RhD typing. CD38 is expressed at very low levels on erythrocytes. Daratumumab binds to the CD38 on erythrocytes, which results in a positive IAT (Indirect Coombs Test). This positive result masks the detection of antibodies to minor antigens and may prevent or delay blood banks from issuing donor blood for transfusion. This effect occurs during daratumumab treatment and for up to 6 months after treatment ends. Subjects will receive a patient identification wallet card for the study that includes the blood profile (ABO, Rh, and IAT) determined before the first infusion of daratumumab along with information on the IAT interference for healthcare providers/blood banks. Subjects are to carry this card throughout the treatment period and for at least 6 months after treatment ends. Blood banks can eliminate the daratumumab IAT interference by treating reagent RBCs with dithiothreitol (DTT) [Chapuy 2015].

Possible methods for blood banks to provide safe RBCs for transfusion to subjects receiving daratumumab include:

- a) Providing ABO/RhD compatible, phenotypically or genotypically matched units
- b) Providing ABO/RhD compatible, K-negative units after ruling out or identifying alloantibodies using DTT-treated reagent RBCs

Uncrossmatched, ABO/RhD compatible RBC units should be administered if transfusion is needed emergently as per local blood bank practice.

Despite daratumumab binding to CD38 on erythrocytes, no indication of clinically significant hemolysis has been observed in daratumumab studies. For additional details, refer to the Daratumumab IB.

### **Pulmonary Function Test**

Subjects with known or suspected COPD must have a FEV1 test during screening. Refer to Section 6.4.2 for details on subjects with higher risk of respiratory complications

### **Vital Signs**

Vital signs (pulse, temperature, and blood pressure) will be performed as specified in Table 3. It is recommended that blood pressure (sitting) and pulse measurements be preceded by at least 5 minutes of rest in a quiet setting without distractions (eg, television, cell phones). Only vital signs associated with an AE will be entered in the eCRF; all measurements will be recorded in the source documents.

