| Vital Signs                   | Vital signs (blood pressure, temperature) measured in sitting position.   | On Cycle 1 Day 1 only: immediately before the start of dara infusion; at 0.5, 1, 1.5, 2, 3.5 hrs after the start of the infusion; at end of infusion; and 0.5,1 hr after end of infusion.

After Cycle 1 Day 1, immediately before infusion start and at end of each daratumumab infusion.  |           |       |  |     |

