### Vital Signs

Descriptive statistics of temperature and blood pressure (systolic and diastolic) values and changes from baseline will be summarized. The percentage of subjects with values beyond clinically important limits will be summarized.

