2.1. Visit Windows

Any analysis that uses time-to-event data will be based on exact determination of time from randomization to the date of the event. For analyses of data by cycle, if data are collected by date (ie, AE onset), the corresponding study evaluations will be assigned to actual sequential cycles, which are derived from the study agent administration data. The start date of a particular cycle is defined as the date of the first scheduled dose, and the end date of a cycle is the start date of the next cycle minus 1. For the last cycle, the end date is defined as the end of treatment visit date or 55 days after the last dose if the end of treatment visit date is not available. If data (eg, laboratory and vital sign, etc) are collected by cycle, the nominal cycle will be used to summarize data.

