6.5. Vital Signs and Physical Examination Findings

Vital signs (systolic and diastolic blood pressure, heart rate, and temperature) values and change from baseline will be summarized at Day 1 each treatment cycle. Similar analyses will be performed for weight at Day 1 of each treatment cycle. Box plots of weight, systolic blood pressure, and diastolic blood pressure over time up to Cycle 20 will be displayed.

A complete physical examination will be performed during the Screening Period. The number of subjects with any medical history will be reported; furthermore, the number of subjects with medical history of special interest will be summarized by pre-specified preferred term.

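### Routine vital signs are kept out of the eCRF, so the planned by-cycle vital-sign summaries, changes from baseline and limit percentages have no adequate data behind them

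*Protocol*

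**What the plan says.** **Measurement.** Protocol 9.5.2 (Vital Signs) says: "Vital signs (pulse, temperature, and blood pressure) will be performed as specified in Table 3". Table 3 requires an extended series on Cycle 1 Day 1 and then: "After Cycle 1 Day 1, immediately before infusion start and at end of each daratumumab infusion".

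**Data entry.** The same paragraph of Protocol 9.5.2 limits what leaves the site: "Only vital signs associated with an AE will be entered in the eCRF; all measurements will be recorded in the source documents".

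**Analysis in the protocol.** Protocol 11.8 (Vital Signs) says: "Descriptive statistics of temperature and blood pressure (systolic and diastolic) values and changes from baseline will be summarized". It adds: "The percentage of subjects with values beyond clinically important limits will be summarized".

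**Analysis in the SAP.** SAP 6.5 covers blood pressure, heart rate and temperature, and says their "values and change from baseline will be summarized at Day 1 each treatment cycle". It also says: "Box plots of weight, systolic blood pressure, and diastolic blood pressure over time up to Cycle 20 will be displayed". SAP 2.1 uses vital signs as an example of per-cycle data: "If data (eg, laboratory and vital sign, etc) are collected by cycle, the nominal cycle will be used to summarize data".

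**The concern.** The analysis sections assume a complete longitudinal dataset: a baseline for each treated subject and a value at each cycle. The data-entry rule creates something different, namely readings present only because an adverse event occurred. A by-cycle mean or box plot from such data does not estimate the vital signs of the treated population. Change from baseline cannot be formed without a baseline.

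Vital signs are one of the protocol's named safety measures, and the safety profile of the three schedules is a secondary objective. The affected tables and plots are descriptive, but a reader of the study report would take them to describe everyone treated.

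**Working it through.** The plan gives no figure to reproduce. The check is whether a routine reading can travel from the bedside to the planned table.

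1. **Route.** Protocol 17.5 has site staff transcribe study data from source to the eCRF. Protocol 17.11 builds the study report from eCRF data and central laboratory transfers. Neither names another feed for pulse, temperature or blood pressure, so a reading not entered in the eCRF does not reach the analysis.
2. **Baseline.** SAP 2.2 takes the closest non-missing value at or before first dosing, using clock time where available. AE collection starts at consent, so a pre-dose reading could be AE-associated, but only if an event was present then. A reading taken during the first infusion is, where timed, too late to be baseline. Most subjects would therefore have no baseline in the database.
3. **Imputation.** SAP 2.4 does not impute missing safety evaluations, so the gap stays.
4. **What the tables expect.** Scheduled Day 1 visits through Cycle 20 number 20 per subject in Arm A, 20 in Arm B and 1 in Arm C (Cycle 1 only). With 40 subjects per arm and full completion: 40 × (20 + 20 + 1) = 1,640 Day 1 visits. Only those with an AE-associated reading would supply a value.
5. **How many subjects contribute.** The documents do not say. Two illustrations for 40 per arm:
   - Assuming 10% of subjects have an event for which vital signs are entered: 0.10 × 40 = 4.
   - If readings during infusion-related reactions are entered, and the 49% rate in Protocol 1.2.2.3 (16 mg/kg monotherapy in earlier myeloma studies) applied here: 0.49 × 40 = 19.6, about 20.

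   Even in the second case the values entered are those around the reaction, not a Day 1 series.
6. **Limit percentage.** SAP 2.5.2 uses the safety set for all safety analyses. With all 40 treated subjects as denominator, the percentage cannot exceed the share contributing a reading: 4/40 = 10% or 19.6/40 = 49%. Readings outside the limits that were not tied to an AE would be missed, so undercounting is the likelier error. With only subjects having a recorded value as denominator, the percentage would describe an AE-selected group.
7. **Scope.** Protocol 9.5.2 does not list weight among the vital signs under this rule and treats it separately under physical examination. The weight summaries and box plot in SAP 6.5 are not shown to be affected.
8. **Parameters.** Protocol 9.5.2 (Vital Signs) names pulse, temperature and blood pressure. Table 3 and Attachment 4 name blood pressure and temperature only, as does the analysis in Protocol 11.8. SAP 6.5 adds heart rate. These do not agree.

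**The case against.** **AE-only entry is a legitimate choice, and one stale sentence may explain the conflict.** The eCRF and its completion guidelines are not available, and SAP 2.1 treats vital signs as collected by cycle, so full collection may in fact have taken place. This stands as a limit on what can be said about the actual database. It does not reconcile the text: if everything is collected, the entry rule in 9.5.2 is wrong and needs correcting.

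**The SAP follows an older protocol version.** It still gives a study end at about 4 years. But the conflict also lies inside the current protocol, between 9.5.2 and 11.8, and the amendment log records no change to the entry rule.

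**The safety loss is limited.** This largely stands. Protocol 9.5.2 requires clinically relevant changes to be recorded in the AE section of the eCRF, and all readings remain in source documents open to monitoring under Protocol 17.8. A reader might infer that events such as the Grade 3 or higher hypertension mentioned in Protocol 1.2.2.3 would go unseen. They would not: such an event is an AE, and its readings are among those entered. What the tables could not show is a shift that nobody judged reportable.

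**The selection should not be exaggerated.** A reader might infer that only abnormal values would be entered, or that the limit percentage would approach 100%. The rule says AE-associated, and a normal blood pressure taken during a cough or nasal congestion may qualify. The percentage depends on an unstated denominator and, with all treated subjects, would more likely be too low. No formal comparison of vital signs between arms is planned.

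**Conclusion.** The plan is wrong as written. Its data-entry rule cannot supply the vital-sign outputs in Protocol 11.8 and SAP 6.5. Baseline and change from baseline would be missing for most subjects, by-cycle summaries and blood-pressure box plots would rest on AE-associated readings, and the limit percentage would probably be undercounted over all treated subjects.

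This rests on the eCRF following Protocol 9.5.2 and on there being no unnamed data feed. The number of contributing subjects is not known; a few to about half per arm is an illustration, and its upper figure borrows a rate from a different population. It would go too far to conclude that every SAP 6.5 output fails, since weight is outside the rule.

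The consequence is confined to descriptive safety outputs. The co-primary endpoints are untouched. A correction is still worth making, because the tables would be largely empty or misread.

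**What to change.** Choose one of two routes.

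**(a) Collect what the tables need.** Amend Protocol 9.5.2 so that baseline and the pre-dose Day 1 reading of each cycle are entered in the eCRF for all treated subjects, in addition to AE-associated values. State in Protocol 11.8 and SAP 6.5 that the summaries use these scheduled readings only. The cost is data entry from source, partly retrospective because the Amendment 5 summary notes that the primary analysis has already been reported. If the Cycle 1 Day 1 pre-dose reading serves as baseline, the load to Cycle 20 is at most 1,640 sets with 40 per arm and full completion. Entering the screening reading as well adds 120, giving 1,760. Extension cycles would add more.

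**(b) Keep AE-only entry.** Replace the pulse, temperature and blood-pressure summaries, the limit percentages and the blood-pressure box plots with a listing of AE-associated readings. Keep the weight summaries and weight box plot. Amend the vital-sign example in SAP 2.1 to match. The cost is text edits only.

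Under either route, align Table 3 and Attachment 4 (blood pressure and temperature) with Protocol 9.5.2 (which adds pulse) and SAP 6.5 (heart rate), so that the parameters measured, entered and analysed are the same.

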### **Physical Examination and ECOG Performance Status**

A complete physical examination (including neurological examination) should be performed during the Screening Phase. Thereafter, only a symptom and disease directed physical examination is required. Height will be measured at screening only; weight will be measured regularly as specified in Table 3. Abnormalities will be recorded in the appropriate sections of the eCRF. ECOG Performance Status (Attachment 1) will be used to evaluate the impact of the disease status on the activities of daily living. When scheduled, ECOG assessments should be obtained prior to any other study procedures planned for the same day.

## **9.6. Sample Collection and Handling**

If blood samples are collected via an indwelling cannula, an appropriate amount (1 mL) of serosanguineous fluid slightly greater than the dead space volume of the lock will be removed from the cannula and discarded before each blood sample is taken. After blood sample collection, the cannula will be flushed with 0.9% sodium chloride, United States Pharmacopeia (or equivalent)/sodium heparin of 10 U/mL and charged with a volume equal to the dead space volume of the lock. If a mandarin (obturator) is used, blood loss due to discard is not expected. Refer to the Table 1 for the timing and frequency of all sample collections.

For samples collected from the central laboratory, sample dates and times must be recorded on the laboratory requisition form. Further instructions for the collection, handling, storage, and shipment of samples are found in the laboratory manual that will be provided. Collection, handling, storage, and shipment of samples must be under the specified, and where applicable, controlled temperature conditions as indicated in the laboratory manual.

## 10. SUBJECT COMPLETION/WITHDRAWAL

### 10.1. Completion of Treatment

A subject will be considered to have completed study treatment if he or she has finished all planned doses of daratumumab in the treatment arm to which they were randomized.

For subjects in Arm A (long intense) and Arm B (intermediate), there is a possibility to extend treatment with IV daratumumab (Q8W) after the end of Cycle 20 if, as per investigator discretion, there is a positive benefit/risk ratio, absence of Grade  $\geq 3$  treatment related toxicity, and at least stable disease has been achieved. In the case of subjects who already completed EOT and end of Cycle 20 occurred  $< 6$  months, these subjects can also continue receiving IV daratumumab administrations every 8 weeks.

For subjects who are treated in the Treatment Extension Phase as of Amendment 5, daratumumab 16 mg/kg IV may be switched to daratumumab 1800 mg SC at the discretion of the investigator at the same dosing (Q8W) schedule. Subjects with a known allergy/intolerance to sorbitol will not be eligible to switch to daratumumab SC.

### 10.2. Completion of Study

A subject will be considered to have completed the study if he or she has finished all protocol-specified procedures before the end of the study, has not been lost to follow up, and has not withdrawn consent for study participation before the end of the study.

### 10.3. Premature Discontinuation of Study Treatment

If a subject's study treatment must be discontinued before the end of the planned number of cycles or during treatment extension/re-initiation, **this will not result in automatic withdrawal of the subject from the study**. After treatment discontinuation, the subject will move into the Follow-up Phase. The End-of-Treatment Visit should be performed, and Follow-up visit assessments should continue as specified in [Table 1](#) (as of Amendment 5, refer to [Attachment 4](#)). If study treatment is discontinued for a reason other than disease progression, then disease evaluations will continue to be performed as specified in [Table 1](#) (as of Amendment 5, refer to [Attachment 4](#)).

A subject's study treatment must be discontinued if:

- The investigator believes that for safety reasons (eg, AE) it is in the best interest of the subject to discontinue study treatment
- The subject becomes pregnant
- The subject (or the subject's legally acceptable representative) withdraws consent for administration of study treatment
- The subject experiences unacceptable toxicity, including IRRs described in [Section 6.4.3](#)
- The subject missed more than 2 consecutive planned doses due to daratumumab-related AEs

- The subject experiences disease progression (please see below).

A subject who experiences a second primary malignancy that cannot be treated by surgery alone must be withdrawn from the study. However, a subject who develops a malignancy that can be cured surgically may continue to receive the assigned study treatment and should continue to be followed for subsequent progression of MM.

**Before subjects discontinue study treatment due to disease progression**, sites will document disease progression (for example by completing a disease progression form or by contacting the IWRS) as soon as possible and within 48 hours. The medical monitor will confirm that treatment should be discontinued. After confirmation from the sponsor, study treatment will be discontinued and the subject entered into Follow-up.

The primary reason for discontinuation of study treatment is to be recorded in the eCRF.

